9. Record of any body fluids or tissue samples retained
10. All other source documents (subject records, hospital records, laboratory records, etc.)
11. All other documents as listed in Section 8 of the ICH consolidated guideline on GCP (Essential Documents for the Conduct of a Clinical Trial)

The Investigator must obtain approval in writing from the Sponsor prior to destruction of any records.

Normally, these records will be held in the Investigator's archives. If the Investigator is unable to meet this obligation, [] or [] must ask the Sponsor for permission to make alternative arrangements. Details of these arrangements should be documented.

E. Confidentiality

Subject names will not be supplied to the Sponsor. Only the subject number and subject initials will be recorded in the CRF, and if the subject name appears on any other document (e.g., pathologist report), it must be redacted before a copy of the document is supplied to the Sponsor. Study findings stored on a computer will be stored in accordance with local data protection laws. The subjects will be told that representatives of the Sponsor, IRB/IEC, or regulatory authorities may inspect their medical records to verify the information collected, and that all personal information made available for inspection will be handled in strictest confidence and in accordance with local data protection and privacy laws, including the Health Insurance Portability and Accountability Act (HIPAA) Guidelines, and the General Data Protection Regulation (GDPR).

The Investigator will maintain a personal subject identification list (subject numbers with the corresponding subject names) to enable records to be identified.

F. Documentation of Study Results

A CRF will be provided for each enrolled subject.

All protocol-required information collected during the study must be entered by the Investigator, or designated representative, in the CRF. Details of CRF completion and correction will be explained to the Investigator. If the Investigator authorizes other persons to make entries in the CRF, the names, positions, signatures, and initials of these persons must be supplied to the Sponsor.

The Investigator, or designated representative, should complete the CRF pages as soon as possible after information is collected, preferably on the same day that a study subject is seen for an examination, treatment, or any other study procedure. Any outstanding entries must be completed immediately after the final examination. An explanation should be given for all missing data.

By signing the completed CRFs, the Investigator or Subinvestigator attests to the accuracy, completeness, legibility, and timeliness of the data collected on the CRF and casebooks.

The Sponsor will retain the originals of all CRFs. The Investigator will retain a copy of all completed CRF pages.

G. Regulatory and Ethical Considerations

G1. Risk Assessment

Based on the safety results of Study EPI-589-14-01 as summarized in the Clinical Study Report, it is not foreseen that subjects will endure any risks greater than minimal at the 500-mg BID dose selected for this study.

G2. Potential Benefits of Trial Participation

This is the first study to better understand EPI-589 target engagement and potential therapeutic benefit in subjects with PD. Therefore, we cannot assure that subjects will benefit from treatment with EPI-589. Potential benefits may manifest in a variety of ways, such as in disease-related parameters, functioning, and quality of life.

G3. Risk-Benefit Assessment

There are no effective and/or approved disease modifying treatments available for PD, although a number of clinical interventions are being researched. Based on disease mechanism, EPI-589 mechanism of action and pre-clinical studies, EPI-589 may hold benefit for patients with PD. This is the first study to better understand EPI-589 target engagement and potential therapeutic

benefit in subjects with PD. In order to further minimize risks, subjects will be closely monitored with a variety of safety measures.

H. Informed Consent

Before being enrolled in the clinical study, subjects must provide written consent to participate after the nature, scope, and possible consequences of the clinical study have been explained in a form understandable to them. The Investigator will not undertake any measures specifically required only for the clinical study until valid consent has been obtained.

An informed consent document that includes both information about the study and the consent form will be prepared and given to the subject. This document will contain all the elements required by the ICH E6 Guideline for Good Clinical Practice and any additional elements required by local regulations and must be in a language understandable to the subject. Where required by local law, the person who informs the subject must be a physician. It should be signed and dated by all the parties concerned including the subject, legal guardian (where applicable), witness (where applicable) and the person obtaining the consent.

A copy of the signed consent document must be given to the subject. The original signed consent document will be retained by the Investigator.

The Investigator must inform the subject's primary physician about the subject's participation in the trial if the subject has a primary physician and if the subject agrees to the primary physician being informed.

Space intentionally left blank

XII. PUBLICATION

A. Use of Study Results

All information concerning the product, as well as any matter concerning the operation of BioElectron Technology Corporation(such as clinical indications for the drug, its formula, methods of manufacture, and other scientific data relating to it, that have been provided by BioElectron Technology Corporation and are unpublished), are confidential and must remain the sole property of BioElectron. The Investigator will agree to use the information only for the purposes of carrying out this study and for no other purpose unless prior written permission from BioElectron Technology Corporation is obtained. The Sponsor has full ownership of the CRFs completed as part of the study.

By signing the study protocol, the Investigator agrees that the results of the study may be used for the purposes of national and international registration, publication, and information for medical and pharmaceutical professionals by BioElectron. If necessary, the authorities will be notified of the Investigator's name, address, qualifications, and extent of involvement.

This Study is part of a multicenter clinical research study. Accordingly, Sponsor will act as coordinator and referee with respect to publications of the data generated thereunder. Principal Investigator shall not publish or disclose any data, result or information with respect to any matters resulting from work performed under this Protocol while this Study is being conducted at other center/s. Only after the completion of this Study at all other centers, provision of the data to the FDA or EMA for review and comment, and publishing the combined data from all of the centers, may the Principal Investigator publish/present the individual results of the Study in accordance with this paragraph.

Principal Investigator may publish provided, however, that no publication, abstract, announcement or disclosure (“Publication”) shall be made until the Principal Investigator submits to Sponsor any proposed Publication for Sponsor’s review. Sponsor shall have a period of sixty (60) days to review such Publication. If Sponsor determines during the review period that the Publication contains patentable subject matter, then the above sixty (60) days shall be extended to one hundred twenty (120) days in order to allow for the preparation of patent applications covering said patentable subject matter. Unless Sponsor approves in writing, no Publication may contain any Confidential Information (other than data and results generated under the Study).

Without limiting the foregoing, Institution and Principal Investigator, and all other study investigators in other study institutions, shall give due regard to Sponsor’s legitimate interests, such as manuscript authorship, coordinating and maintaining the proprietary nature of submissions to health authorities, and coordinating with other ongoing studies in the same field, and agree to accept Sponsor’s reasonable comments and suggestions with respect to such Publications.

If the Investigator is to be an author of a publication manuscript prepared by BioElectron Technology Corporation, BioElectron will allow the Investigator or CRO 60 days for full review of the manuscript before publication.

Space intentionally left blank

XIII. LIST OF ABBREVIATIONS

AE	adverse event
AI	accumulation index
ALT	alanine aminotransferase
AST	aspartate aminotransferase
AR	accumulation ratio
BDI	Beck Depression Inventory
BID	twice daily
BSO	L-buthionine-(S,R)-sulfoximine
C-SSRS	Columbia-Suicide Severity Rating Scale
CBC	complete blood count
CFR	Code of Federal Regulations
CK	creatinine kinase
CNS	central nervous system
CoQ10	Coenzyme Q 10
CRF	Case Report Form
CRO	Contract Research Organization
CTC	Common Terminology Criteria
CTCAE	Common Terminology Criteria for Adverse Events
DaT	dopamine transporters
DSMB	data safety monitoring board
ECG	electrocardiogram
EDTA	ethylenediaminetetraacetic acid
EITT	efficacy intent-to-treat
EPDA	European Parkinson's Disease Association
EU	European Union
%F	percent fluctuation
FDA	Food and Drug Administration
GCP	Good Clinical Practices
GCRC	good clinical research practice
GDPR	General Data Protection Regulation
GSH	glutathione
GSSG	glutathione disulfide
HDPE	high density polyethylene
hERG	human Ether-a-go-go Related Gene
HCG	human chorionic gonadotropin
HIPAA	Health Insurance Portability and Accountability Act
HMPAO	hexamethylpropylene amine oxime
ICF	informed consent form
ICH	International Committee on Harmonization
IEC	Independent Ethics Committee
IND	Investigational New Drug
INR	International Normalized Ratio
IRB	Institutional Review Board
IUPAC	International Union of Pure and Applied Chemistry

kg	kilogram
Λ_z	apparent terminal constant
LFT	liver function test
MAD	multiple ascending (oral) dose
MADRS	Montgomery and Asberg Depression rating scale
MCH	mean corpuscular hemoglobin
MCHC	mean corpuscular hemoglobin concentration
MCV	mean corpuscular volume
MDS-UPDRS	Movement Disorder Society-sponsored revision of the Unified Parkinson's Disease Rating Scale
mg	milligram
mL	milliliter
MoCA	Montreal Cognitive Assessment
MPTP	1-methyl-4-phenyl-1,2,3,6-tetrahydropyridine
MPV	mean platelet volume
mtDNA	mitochondrial DNA
N/A	not applicable
NADPH	nicotinamide adenine dinucleotide phosphate
NF	National Formulary
nM	nanomolar
NMSS	Non-motor Symptoms Scale
NOAEL	no observed adverse effect level
NQO1	NAD(P)H Quinone oxidoreductase 1
OD	once daily
OTC	over-the-counter
PD	Parkinson's disease
PDQ-39	39-Item Parkinson's Disease Questionnaire
PO	by mouth
PT	Prothrombin Time
PTT	Partial Prothrombin Time
PVP	polyvinylpyrrolidone
QT	interval between the start of the Q wave and the end of the T wave
RBC	red blood cell
RDW	red cell distribution width
SAD	single ascending (oral) dose
SAE	serious adverse event
SD	standard deviation
SUSAR	suspected unexpected serious adverse reaction
$t_{1/2}$	half-life
T_{max}	time to peak concentration
ULN	upper limit of normal
USP	United States Pharmacopeia
UV	ultraviolet

XIV. SIGNATURE OF SPONSOR

A. Declaration of Sponsor

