9. BDI
10. MADRS
11. Timed motor tests as ON state only (for subjects on dopamine therapy)
12. Pharmacokinetics

C. Secondary Endpoints (Safety)

1. Routine assessments of AEs and SAEs
2. Dose limiting toxicities
3. Routine serum chemistries with liver function tests

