4. C-SSRS
5. Routine hematology tests with coagulation tests
6. Electrocardiogram

D. Screening and Baseline Evaluation

D1. Physical Examination, height and weight

Complete physical exams will be conducted (excluding genital/rectal exam) at protocol specified study visits. The physical examination will consist of an examination of the following: general appearance, skin, head, eyes, ears, nose, throat, neck (including thyroid), lymph nodes, chest, heart, abdomen, and extremities.

Vital sign measurements (pulse rate, blood pressure and respiration rate) will be obtained in the sitting position (after the subject has been sitting for five minutes).

The findings from breast exam will be captured as part of the screening physical exam. The findings from breast exams conducted within 6 months of the screening visit and those collected as part of medical history, may be used for the screening physical exam.

Medical history and demographics including age, gender, race, will be collected at screening visit. Weight (kg) will be measured in ordinary indoor clothing (i.e., street clothes, scrubs, etc.) with shoes off. Height will be recorded in centimeters (cm) and need not be repeated after screening visit.

If clinically significant findings, as determined by the Investigator, are recorded for a particular symptom, sign or abnormal measurement, that measurement will be repeated at medically appropriate intervals until the value returns to an acceptable range, a specific diagnosis is established, or the condition is otherwise explained.

D2. Laboratory Evaluations

Subjects will have less than 100 mL of blood drawn over the course of the study.

The following variables will be collected at various times (as detailed in Section I).

- a. Hematology
 - a. Erythrocytes: red blood cell (RBC) count, hematocrit, hemoglobin, mean corpuscular volume (MCV)
 - b. Leukocytes: white blood cell count (WBC) and differential (basophils, eosinophils, lymphocytes, monocytes, and neutrophils). The differential can be recorded as an absolute value or percentages.
 - c. Platelets: platelet count
 - d. Coagulation: prothrombin time (PT) with INR, and partial thromboplastin time (PTT)
- b. Serum chemistry
 - a. Liver: Alkaline Phosphatase (ALP), ALT (serum glutamic-pyruvic transaminase [SGPT]), AST (serum glutamic-oxaloacetic transaminase [SGOT]), bilirubin (total and direct), gamma-glutamyl transferase (GGT), and lactic dehydrogenase (LDH)

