 - b. Renal: blood urea nitrogen (BUN), and creatinine
 - c. Electrolytes: sodium, potassium, chloride and bicarbonate
 - d. General: creatine phosphokinase (CPK), total protein, albumin, calcium, magnesium, glucose, phosphate
 - e. Lipids: cholesterol (total), high-density lipoprotein (HDL) cholesterol, low-density lipoprotein (LDL), cholesterol, and triglycerides

- c. Urine pregnancy test
 - 1. Human chorionic gonadotropin (HCG) beta subunit will be measured on all female subjects of childbearing potential.

Laboratory tests that result in significantly abnormal values should be repeated for verification. Additional tests and other evaluations required to establish the significance or etiology of an abnormal result, or to monitor the course of an AE, should be obtained when clinically indicated. In particular, if a clinically significant abnormal result is observed that is not resolved by the final study visit, repeat tests should be performed to document resolution or stability of the abnormality.

Diagnoses associated with any NIH Common Terminology Criteria for Adverse Events (CTC v4.03) Grade 3 or 4 laboratory abnormalities will be recorded as adverse events (AEs) on the CRF. The recorded event should indicate the underlying abnormality or diagnosis (e.g., renal insufficiency) if known, as opposed to the observed deviation in laboratory results (e.g., elevated creatinine). Any additional relevant laboratory results obtained by the Investigator during the study will be supplied to the Sponsor.

D3. Dose Limiting Toxicity (DLT)

There were no DLTs noted in the phase 1 study; the dose-limiting (NOAEL) in nonclinical studies, as described in the protocol were increased LFTs (ALT, AST), rhabdomyolysis (elevated CPK), renal dysfunction (likely secondary to rhabdo), and marrow toxicity (most notably hemolysis). Therefore for this study, any increased LFT, BUN/Cr or CPK (or CK) should be considered related to study drug and should be designated as a DLT. If there is a DLT, a dose reduction will be attempted. Contact the medical monitor for further instructions.

D4. Columbia Suicide Severity Rating Scale (C-SSRS)

The C-SSRS is a semi-structured tool for assessing suicidal ideation (Questions 1-5) and behavior (Questions 6-10) through a series of questions.

E. Sample Collection Procedures, Bioanalytical Methods and Sample Shipment

Subject samples will be identified by unique sample codes.

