In the US, all fatal or life-threatening suspected unexpected serious adverse events assessed as possibly or probably related to study drug by the Sponsor must be reported to the FDA as soon as possible (i.e., by telephone or facsimile transmission), but no later than 7 calendar days after first knowledge by the Sponsor that a report qualifies as a suspected unexpected fatal or life-threatening reaction. All unexpected serious adverse events, other than fatal or life-threatening, assessed as possibly or probably related to study drug by the Sponsor must be reported to the FDA within 15 calendar days from the day the Sponsor determines that the information qualifies as a SUSAR.

In the UK, the Sponsor or trial investigator must act immediately or at least within 24 hours after becoming aware of a SUSAR by informing the MHRA's Clinical Trial Unit by telephone. The MHRA must then be informed in writing within 3 days of the incident. All SUSARs originating in the UK or originating outside the UK involving the same medicinal product are to be reported. Fatal or life-threatening SUSARs are to be reported as soon as possible, but no later than after 7 days. Any additional relevant information must be sent within 8 days of the report. Non-fatal or non-life-threatening SUSARs are to be reported as soon as possible but no later than 15 days after becoming aware of the reaction.

C8. Follow-up Report

If an SAE has not resolved at the time of the initial report, a follow-up report including all relevant new or reassessed information (e.g., concomitant medication, medical history) should be submitted to the IRB/ IEC . All SAEs should be followed until either resolved or stable.

C9. Dose Modification Guidelines

In the event that any patient develops elevated INR \geq grade 2 in severity ($> 1.5-2.5 \times \text{ULN}$) per CTCAE criteria version 4.0 thought to be related to treatment with EPI-589, administration of EPI-589 will be reduced by 1/2 to 50 percent of the starting dose. Should the INR toxicity not resolve to at least grade 1 in severity within two weeks of the initial dose reduction, administration of EPI-589 may either be further reduced or discontinued.

Once a patient's dose is reduced due to elevated INR thought to be related to study drug administration, their dose should not be re-escalated.

D. Medical Emergencies

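### The DLT definition in VII.D3 omits the related INR elevation for which X.C9 mandates a dose cut, so an isolated INR dose reduction is not counted in the DLT endpoint

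*Protocol*

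**What the plan says.** Section VII.C of the Protocol lists "Dose limiting toxicities" as the second secondary safety endpoint. The synopsis also names it among the safety variables.

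VII.D3 says what a DLT is: "any increased LFT, BUN/Cr or CPK (or CK) should be considered related to study drug and should be designated as a DLT". It sets no grade, and it presumes the causal link instead of asking for a judgement. On dosing it adds: "If there is a DLT, a dose reduction will be attempted". The size of the reduction is not given, and the site is referred to the medical monitor.

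X.C9 (Dose Modification Guidelines) deals with a different laboratory finding. It begins "In the event that any patient develops elevated INR" and applies at CTCAE grade 2 or higher. When the elevation is attributed to the drug, "administration of EPI-589 will be reduced by 1/2 to 50 percent of the starting dose". If the INR has not come back to grade 1 within two weeks, the dose may be lowered further or stopped. A dose reduced for this reason is not raised again.

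X.C9 does not use the term DLT and does not mention VII.D3. VII.D3 does not mention INR or X.C9.

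**The concern.** The term suggests that a DLT count covers the subjects whose dose had to be limited because of toxicity. X.C9 is the only rule in the protocol that combines a severity grade, a causal judgement and a stated size of dose reduction, yet the event it describes is absent from the endpoint definition. Meanwhile a liver-test rise of any size, with no causal judgement, is a DLT.

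What is at stake is the meaning of the reported count. The protocol uses the absence of DLTs as a summary safety statement: III.D1 says none has been reported in humans so far, and VII.D3 opens by noting none in phase 1. Under the current text this trial could report no DLT although a subject's dose had been halved for INR toxicity attributed to the drug.

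This is not a detail that can simply be left to an analysis plan. VII.D3 tells sites which events to designate as DLTs when they occur, and later tabulation starts from those designations.

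**Working it through.** The plan states no figure to reproduce. The check sets the sections side by side.

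**Inputs**
- Endpoint: VII.C, item 2 of the secondary safety endpoints.
- Definition: VII.D3, naming LFT, BUN/Cr and CPK (or CK).
- Laboratory panels: VII.D2. INR is listed with prothrombin time under hematology, coagulation. The liver panel is ALP, ALT, AST, bilirubin, GGT and LDH.
- Dose rule for INR: X.C9.
- Planned size: VIII.D, about 40 subjects, with up to 20 more under the adaptive part.

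**Could "LFT" in VII.D3 cover INR?** Not on the protocol's own grouping. VII.D2 keeps INR out of the liver panel.

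**How each type of event is classified**
1. Any isolated rise in a liver test, BUN/creatinine or CPK: a DLT under VII.D3. X.C9 does not apply.
2. Isolated INR elevation, grade 2 or higher, attributed to EPI-589: X.C9 applies and the dose is halved without re-escalation. VII.D3 does not list it, so it is not designated a DLT.
3. Both together: a DLT through the VII.D3 finding, so the count is right. The subject now falls under two dose texts: an attempted reduction of unstated size with referral to the medical monitor (VII.D3), and a fixed reduction without re-escalation (X.C9). Nothing says how they relate.
4. INR elevation below grade 2, or not attributed to the drug: neither section applies.

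The counting gap is case 2. The unreconciled dose text is case 3.

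**Scale of one uncounted subject**
- At the planned size: 1/40 = 0.025, or 2.5 percentage points.
- With all 20 adaptive subjects: 1/60 = 0.017, or 1.7 percentage points.

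The protocol gives no INR event rate, so the expected number of such subjects cannot be calculated.

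**The case against.** VII.D3 does not say that nothing else can be a DLT. It can be read as a rule of mandatory attribution for the organ toxicities seen in animals, and INR is not among those findings. This is fair: the omission is inferred from VII.D3 being the sole definition, not from an express exclusion. But no other text would lead a site to designate an INR event as a DLT.

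A reader might infer that tolerability at 500 mg BID will be understated. The documents do not support that. X.A sends adverse events arising from clinically significant laboratory findings to the CRF, coagulation tests are a secondary safety endpoint in their own right, and VIII.C examines coagulation data by name. VIII.C specifies no DLT rate or DLT-based decision. VII.D3's ungraded triggers may also push the overall count upward, so the net direction is unknown.

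A reader might also infer that the two sections contradict each other for every subject. They do not: their triggers are disjoint, and an isolated event falls under only one. The difficulty arises only when both occur.

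Two cautions bear on the remedy. Defining a DLT as whatever triggers a reduction under VII.D3 would be circular, because there the DLT triggers the reduction. And calling the INR event a DLT without qualification would attach VII.D3's dose instruction to it. Both stand, and the fix is worded to avoid them.

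Finally, VII.D3 lists marrow toxicity with hemolysis among its nonclinical grounds and then leaves it out of the designation. That is a separate gap and does not remove this one.

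**Conclusion.** The point holds in a limited form. The only DLT definition leaves out a drug-attributed toxicity for which the protocol mandates a dose cut, so the secondary DLT endpoint, applied literally, misses subjects reduced for isolated INR elevation. It also leaves subjects with both kinds of event under two dose-reduction texts that do not refer to each other.

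The conclusion rests on reading VII.D3 as the complete definition and on VII.D2's grouping of INR outside the liver tests. The effect is confined to the DLT count; the events are still reported elsewhere in the safety data. Neither the number of such cases nor the net bias in the DLT count can be derived from the protocol, and the per-subject shares above show scale only. The point is worth correcting because the repair is cheap, not because a large distortion has been shown. Which dose text is clinically right is not judged here.

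**What to change.** Add one sentence to VII.D3, expressly limited to tabulation of the endpoint: subjects whose dose is reduced or stopped under X.C9 are counted in the DLT endpoint alongside the VII.D3 laboratory events and shown on a separate line. The sentence should say that it governs counting only, so that it does not extend VII.D3's dose instruction to INR events. A subject with both kinds of event should count once in the total.

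Add a cross-reference in each direction between VII.D3 and X.C9, so that the sponsor reconciles the two dose-reduction texts for a subject who meets both. No dose, threshold or clinical rule is proposed.

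The cost is one sentence, two references and one table row. Adding the INR cases can only raise the total or leave it unchanged, and it joins a graded, attributed event with ungraded ones. The separate line keeps the two visible.
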